## (3) Incidence of air leakage

**Justification for selection:** Air leakage is a common complication of lung tissue anastomosis, which will increase the risk of subjects. Therefore, the "occurrence rate of air leakage" is selected as one of the safety indicators for product evaluation. At the same time, with reference to the *Guidelines for Technical Review of Endoscopic Stapler Registration* issued by China Food and Drug Administration on March 13, 2017, the "incidence rate of air leakage" is selected as a safety evaluation indicator for such products.

**Evaluation time:** During the surgery.

**Evaluation mode:** After the completion of cutting and anastomosis of lung tissues, the investigators drip normal saline to the staple line to see whether there are bubbles, which is used as the basis for judging air leakage.

Formula: Incidence of air leakage = number of subjects with air leakage/total number of subjects in the group  $\times 100\%$ 

## (4) Incidence of Staple Line Infection

Justification for Selection: Staple line infection is a common complication of lung tissue stapling procedures and poses an increased risk to the subject. Therefore, "the incidence of staple line infection" is

selected as one of the indicators to evaluate the product safety.

Evaluation time: from the end of surgery to the end of follow-up.

**Mode of evaluation:** The clinician judges whether the subject has a staple line infection based on the symptoms, signs, endoscopy, angiography, etc.

**Formula:** Incidence rate of staple line infection = eligible subjects in each group/total number of subjects in the group  $\times 100\%$ 

#### (5) Incidence of SAEs

Lobectomy (segmentectomy)

**Evaluation time:** During the whole clinical trial process.

**Evaluation method:** Serious adverse event refers to events occur in the process of clinical trial that causes death or serious deterioration of health, including fatal disease or injury, permanent damage to the body structure or body function, requiring hospitalization or prolonging the hospitalization, requiring medical or surgical intervention to avoid the permanent damage to the body structure or body function.

**Formula:** SAE incidence = number of subjects with SAE in this group/number of all subjects in this group  $\times$  100%.

**Precautions:** The adverse events related to the staple line during clinical trial shall be considered as serious adverse events. Since "staple line repair" may be associated with "staple line dehiscence", the "staple line repair "is not repeatedly considered a serious adverse event.

#### (6) Incidence of AE (adverse event)

Evaluation time: During the whole clinical trial process.

Formula: Incidence of adverse events = number of subjects with adverse events in this group/number of all subjects in this group  $\times$  100%.

**Definition:** An adverse event is any untoward medical occurrence in a clinical investigation, whether or not related to the device. It is necessary to analyze the postoperative vital signs and laboratory tests (blood routine, biochemical indicators, etc.).

#### (7) Incidence of device defects

**Definition:** An test device defect that occurs during the course of a clinical trial. "Staple pop" due to human factors (e.g., incorrect reload selection) is not a defect of the device.

Measurement time: During the whole process of clinical trial.

**Calculation formula:** Incidence of device defect = number of device defects/total number of devices  $\times$  100%.

#### 8.1.9 Operational performance evaluation

#### (1) Stapler operating performance evaluation

Measurement time: During the stapler operation process.

**Evaluation method:** ① Whether the single-handed operation of stapler is smooth; ② whether the stapler can fire normally; ③ whether the back-off is smooth after the completion of anastomosis, whether there is tissue entrapment, whether there is resistance; ④ whether the stapler can fire continuously for many times is reliable; ⑤ whether the stapler can completely cut off the tissue; ⑥ whether the battery supply is stable; ⑦ whether the electric cutting is smooth.

#### 8.2 Test Process

#### 8.2.1 Test Flow Chart

Visit Time	Visit 1	Visit 2	Visit 3	Visit 4	
	Before surgery	During surgery	After surgery	After surgery	
Visit Item	(Day -7 ~ 0)	(Day 0)	(Day $7 \pm 2$ days)	(Day $30 \pm 5$ days)	
Informed consent					
Subject screening					
Demographic data					
History of present illness					
Past medical history					
Vital signs					
Blood routine					
Coagulation routine					
Blood biochemistry					
Cardiac examination					
Pulmonary function test					
Arterial blood gas analysis	▲				
Preoperative imaging					
Blood pregnancy test 					
Randomization					
Intraoperative		_			
observation record		_			
Use of device					
Postoperative imaging 					
Postoperative follow-up					
observation					
Concomitant medication					
Adverse events					
Device defect					

1 Only for women of childbearing potential.

2 In case of anastomotic leakage and bleeding, the investigators may perform relevant examinations for the subjects according to actual needs.

#### 8.2.2 Enrollment

The investigators screened the subjects according to the inclusion and exclusion criteria after obtaining their informed consent; on the day of conducting total-thoracoscopic anatomic lobectomy (segmentectomy), the subjects were randomly divided into the test group and the control group according to the random assignment instructions.

#### 8.2.3 Randomization

The trial was stratified by clinical trial institutes with the randomization method of stratified blocks. The seed number and block length were determined with SAS9.1 statistical software programming. The subjects were divided into the test group and the control group in a ratio of 1:1. The random grouping arrangement of at least 164 subjects was generated, and the corresponding sequentially numbered, opaque and sealed randomization envelopes were made. The randomization envelopes were kept and allocated by relevant personnel who were not involved in the screening and treatment of subjects and authorized by the investigator.

The random number is a 4-digit sequential number consisting of "center number" and "serial number". The first digit is the number of the clinical trial institution, and the last 3 digits are the "serial number" assigned by randomization. When the serial number is less than 3 digits, add "0" to make up 3 digits. If the randomization number "1001" is the first randomization number of the clinical trial institute with the institute number of 01, it corresponds to the first subject randomized at the institute.

When a subject was determined to be enrolled, the investigators or other authorized designee requested randomization assignment from the randomization envelope manager. The randomization envelope keeper took out the randomization envelope in the order of random number, filled in the screening number and initials of the subject to be assigned to the designated place on the back of the envelope, and signed the name and date to complete the allocation. The investigators or other authorized designee then intervened based on the results of the randomization assignment (i.e., test groups).

#### 8.2.4 Blinding method

The investigators could not be blinded due to the difference in appearance between the test device and the control device, this trial therefore adopted an incomplete blinding method, and the subjects were not informed of the randomization results (i.e., the subjects did not know their own treatment assignment).

#### 8.2.5 Inspection items

#### 8.2.5.1 Medical history and vital signs

- (1) Demographic data: gender, date of birth;
- (2) History of present illness: admission time, cause;
- (3) Past medical history: allergy history, dysfunction history of vital organs (heart, lung, liver and kidney), surgery history, and previous medication history  (within 1 month);
- (4) Vital signs: height, weight, blood pressure, pulse, temperature, respiration, BMI;

### 8.2.5.2 Laboratory examinations 

- Blood routine: hemoglobin (Hgb), red blood cell count (RBC), white blood cell count (WBC), neutrophil count (NEUT), neutrophil ratio (NEUT%), platelet count (PLT);
- (2) Coagulation blood routine: prothrombin time (PT), activated partial thromboplastin time (APTT), international normalized ratio (INR);
- (3) Cardiac examination: ECG, cardiac ejection fraction;
- (4) Blood biochemistry: aspartate aminotransferase (AST), alanine aminotransferase (ALT), serum total bilirubin (STB), serum albumin (ALB), serum creatinine (Scr), blood urea nitrogen (BUN);
- (5) Pulmonary function test: forced expiratory volume in one second (FEV1)/predicted value, forced expiratory volume in one second (FEV1)/forced vital capacity (FVC);
- (6) Arterial blood gas analysis: pH, oxygen partial pressure, carbon dioxide partial pressure, oxygen saturation (SpO2);
- (7) Blood pregnancy test: applicable to women of childbearing age  $(18 \sim 50 \text{ years old})$ ;

#### 8.2.5.3 Preoperative imaging 

 CT/MRI examination: whether there is pleural adhesion and is to what extent, whether there is hilar significantly calcified lymph node;

#### 8.2.5.4 Postoperative imaging examination 

- (1) Angiography: whether there is staple line bleeding;
- (2) Thoracoscopy: whether there is air leakage, whether there is staple line bleeding;

#### 8.2.5.5 Other examinations

(1) Intraoperative observation items: operation starting time, operation ending time (24 h clock h/min) , anastomosis starting time, anastomosis ending time (s), resected lobe or segment , intraoperative blood

 Mainly record drugs that affect healing (e.g., antineoplastic agents, corticosteroids) or coagulation.

 Body mass index (BMI) = weight (kg)  $\div$  height (m^2)

 For laboratory examinations, the reports/results issued by our hospital within 7 days prior to surgery can be accepted.

 For imaging examination, the reports/results issued by our hospital within 1 month prior to surgery can be accepted.

 In case of air leakage and bleeding at the staple line, the investigators may decide whether the subject will receive

relevant examinations according to actual needs.

 The duration from the time of thoracotomy to chest closure is recorded.

 Right upper lobe, right middle lobe, right lower lobe, left upper lobe and left lower lobe.

loss, whether the transection and anastomosis are successful, whether the cutting staple line is complete, whether there is leakage in the cutting staple line, whether there is bleeding in the cutting staple line, whether there is air leakage in the staple line, whether there is conversion to thoracotomy , number of stitches for staple line repair , whether there is staple line dehiscence , whether there are other complications , evaluation on the stapler operating performance;

- (2) Use of device : models and specifications of electric-endoscopic stapler, reload models and specifications, device defect;
- (3) Postoperative follow-up observation: whether there is anastomotic line bleeding , whether there are other complications , duration of chest tube drainage (days), whether there is anastomotic infection;
- (4) Routine observation items: adverse events/serious adverse events, concomitant and combined medication, protocol deviations.

### 8.2.6 Device using specification

According to the results of random allocation, the investigators apply the study medical device to the subjects who enter the test group, and the control medical device to the subjects who enter the control group.

### 8.2.7 Visit schedule

Subjects should receive 4 visits before the end of the study: before surgery (Day  $-7 \sim 0$ ), during surgery (Day 0), on Day  $7 \pm 2$  after surgery, and on Day  $30 \pm 5$  after surgery.

## 8.2.7.1 1st visit 1/before surgery (Day $-7 \sim 0$ )

- (1) The ICF form shall be signed;
- (2) Screening subjects according to the inclusion and exclusion criteria;
- (3) Randomized grouping;
- (4) Recording demographic data, current medical history and past medical history are recorded;
- (5) Examining vital signs;
- (6) Performing preoperative imaging examination (CT/MRI examination);
- (7) Performing laboratory examinations (blood routine, coagulation routine, blood biochemistry, heart examination, pulmonary function test, arterial blood gas analysis, blood pregnancy test);

 If yes, please specify the reason and whether it is related to the stapler. If the investigators use other devices for repair, it is necessary to record the product name and the quantity used, and finally replace the number of repair needles with the quantity used.

 Truthfully record the model and amount used in the clinical trial.

 If corresponding symptoms occur, the reasons for confirming the event should also be briefly described, so as to facilitate the review. The diagnosis is confirmed by thoracoscopy or second surgical exploration.

- (8) Recording concomitant and concomitant medications;
- (9) Recording protocol deviations;

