## 6.2 Contraindications

- Do not use the instruments on the aorta.
- Do not use the instruments on ischemic or necrotic tissue.
- Do not use any linear cutter on major vessels without making provision for proximal and distal control.
- Tissue thickness should be carefully evaluated before firing any stapler. Refer to Reload Product Codes for tissue compression requirement (closed staple height) for each staple size. If tissue cannot comfortably compress to the closed stale height, or easily compresses to less than the closed staple height, the tissue is contraindicated as it may be too thick or too thin for the selected staple size.
- These instruments are not intended for use when surgical stapling is contraindicated.

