#### 8.1.6.3 Exclusion criteria

#### Subjects meeting any of the following conditions can not be included:

- (1) Subjects are with video-assisted thoracoscopic surgery-related contraindications;
- Subjects' preoperative imaging findings indicate severe pleural adhesions and significantly calcified hilar lymph nodes;
- (3) Subjects with platelet (PLT)  $< 60 \times 10^{9}$ /L or international normalized ratio (INR) > 1.5;
- (4) Subjects with forced expiratory volume in one second (FEV1)/predicted value  $\leq$  50%, or forced expiratory volume in one second (FEV1)/forced vital capacity (FVC)  $\leq$  60%;
- (5) Subjects with ejection fraction  $\leq 50\%$ ;
- (6) Subjects with major organ failure or other serious diseases (including clinically relevant cardiovascular disease or myocardial infarction within 12 months prior to enrollment; severe neurological or psychiatric history; preoperative severe infection that must be controlled by medication; active disseminated intravascular coagulation; high risk of thrombosis);
- (7) Subjects who are pregnant or lactating women;
- (8) Subjects participating in other drug or device clinical trials within 1 month before the trial;
- (9) Other situations not suitable for inclusion judged by the investigators.

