#### 9.4 Expected Dropout Rate

Version No.: 1.1/Version date: 20190325 Clinical Trial on Performance and Safety of Disposable Powered Articulating Endoscopic Linear Cutter Stapler in Total-Thoracoscopic Anatomic Lobectomy (segmentectomy)

A 20% dropout rate is expected during sample size estimation.

This drop-out rate refers to the proportion of subjects who finally can not be included in the primary analysis. Drop-out subjects refer to those confirmed by the principal investigator with serious protocol violation (affecting the main evaluation/efficacy evaluation). The following conditions may be included, but not limited to: the subject violates the inclusion and exclusion criteria; the subject does not receive any study device; the subject receives the concomitant medication/device prohibited by the protocol; the data of main evaluation indicators are missing; the subject fails to obtain any data after randomization; the subject fails to complete the follow-up visit according to the regulations.

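### The time of randomisation is stated inconsistently: the Visit 1 list allows it up to a week before surgery and places it ahead of the eligibility tests, while 8.2.2 puts it on the day of surgery

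*Combined protocol and SAP*

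**What the plan says.** Four parts of the protocol bear on when a subject is randomised.

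- **8.2.7.1 (Visit 1, Day -7 to 0)** lists consent, then screening, then "3) Randomized grouping". Further down come "6) Performing preoperative imaging examination (CT/MRI examination" and "7) Performing laboratory examinations (blood routine, coagulation routine, blood biochemistry, heart examination, pulmonary function test"; step 7 also includes blood gases and the pregnancy test.
- **8.2.7.2 (Visit 2, Day 0)** has seven items and none is randomisation.
- **8.2.2** has the investigators screen after consent and then, "on the day of conducting total-thoracoscopic anatomic lobectomy (segmentectomy), the subjects were randomly divided into the test group and the control group".
- **8.1.3 (3)** says that randomisation takes place ahead of surgery and applies to subjects who have passed screening. **8.2.3** has the envelope requested once enrolment of the subject has been decided.

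On what follows, 9.4 names among the grounds for not being in the primary analysis: "the subject violates the inclusion and exclusion criteria; the subject does not receive any study device". Section 9.9 limits the FAS to subjects treated at least once with the device. It takes the PPS from the FAS by removing serious deviations and names the PPS as the primary population for efficacy analysis. Sections 8.1.3 (4) and 8.2.4 say that the investigators know the allocation.

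**The concern.** Someone running the study from the visit schedule finds randomisation only at Visit 1, listed third. Taken as a work sequence, that permits an envelope to be opened up to 7 days before surgery, and before the CT, INR, ejection fraction or lung-function result is known. Exclusion 2, for example, turns on whether "preoperative imaging findings indicate severe pleural adhesions and significantly calcified hilar lymph nodes", which cannot be settled until the imaging has been read.

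If a result then excludes the patient, or the patient is not treated, the patient has already been randomised. Whether to re-judge eligibility, proceed, or not use the allocated device is then decided by people who know the arm, and the patient can leave the analysis as a result. That is selection after randomisation in a non-inferiority trial. The longer the gap between allocation and surgery, the more room there is for it. This source of loss is avoidable.

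**Working it through.** **1. Timing statements side by side**

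| Section | When | Condition stated |
|---|---|---|
| 8.1.3 (3) | ahead of surgery | screening passed |
| 8.2.2 | day of surgery | after screening |
| 8.2.3 | no day given | enrolment decided |
| 8.2.7.1 | Day -7 to 0, step 3 of 9 | after step 2 (screening), before steps 6 and 7 |
| 8.2.7.2 | Day 0 | no randomisation step |

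Day 0, before surgery, satisfies every row. Days -7 to -1 satisfy 8.1.3 and 8.2.7.1 but not 8.2.2. No sentence says outright that exclusion results must be on file before the envelope is opened.

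**2. Exclusions that depend on tests listed after step 3**

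- Exclusion 2: adhesions and calcified hilar nodes (imaging, step 6).
- Exclusion 3: platelets and INR (step 7).
- Exclusion 4: FEV1 measures (step 7).
- Exclusion 5: ejection fraction (cardiac examination, step 7).
- Exclusion 7: pregnancy (step 7).

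That is five of the nine exclusion criteria.

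**3. What happens to a patient allocated too early**

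- Found ineligible and not treated: outside both the FAS and the PPS (9.9).
- Found ineligible but treated: may stay in the FAS. Leaves the PPS if the deviation is judged serious; 16.1.3 (1) classes it as significant and 9.4 lists it.

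**4. The plan's own figures**

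Inputs from 9.2.1: success 97% in both arms, margin 10 points, one-sided alpha 0.025, power 80%, drop-out 20%.

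- n3 = 2 × 0.97 × 0.03 × (0.842 + 1.960)² / 0.10² = 45.68.
- n4 = n3 × {1 + [1 + 4/(0.10 × 45.68)]^0.5}² / 4 = 64.12, rounded up to 65.
- 65 / 0.80 = 81.25, rounded up to 82 per arm, 164 in total.

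The plan's 65, 82 and 164 are reproduced. The allowance is 82 - 65 = 17 per arm, or 34 of 164, for losses of all kinds.

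Power by normal approximation with continuity correction is Φ[(0.10 - 1/n) / √(2 × 0.97 × 0.03 / n) - 1.960]. This gives 90.9% at n = 82 and 80.7% at n = 65. Using the whole allowance still leaves the planned power, so the issue is bias.

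**5. What can be said about numbers**

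The documents give no rate of screening failure after allocation and no rate of non-receipt of the device. In the planning series of 160 (9.2.1), all patients had surgery with the stapler, so it shows no case of non-receipt.

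**6. Effect of one lost patient on an arm's rate**

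An excluded patient leaves the numerator and the denominator. Losing a success: 80/82 = 97.56% becomes 79/81 = 97.53%, a shift of 0.03 points.

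**The case against.** The strongest reply is that the documents already place allocation after screening. Sections 8.1.3, 8.2.2 and 8.2.3 say so, and within 8.2.7.1 itself screening is step 2, which cannot be completed without the test results. Demographic data are step 4 although age is an inclusion criterion, so the list reads as a checklist rather than a sequence. In both flow charts the randomisation row comes after all the tests. Footnotes 5 and 6 accept laboratory reports from the 7 days before surgery and imaging from the month before, so results may already be in hand at Visit 1. All of this stands. A reader might infer a flat contradiction, or an instruction to randomise before testing; the documents support neither.

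A reader might also infer that allocation must wait for thoracoscopic exploration. The documents do not require this. The tissue-thickness contraindication in 6.2 is a check on the selected staple size at firing and does not define who is eligible. The planning series had 7 non-stapler conversions in 160. Four were pulmonary artery or vein bleeding during surgery, which exploration would not screen out. At most 3 (two nodal, one anatomical) were of a kind that exploration might reveal, about 164 × 3/160 = 3.1 patients here across both arms. Randomising before exploration is a legitimate choice.

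Lastly, a reader might value each lost patient at 1/82 = 1.2 points against the margin. That would need the lost patient to be a failure. Under 8.1.7.1 a failure by conversion must be caused by the stapler, so a patient never stapled is not a defined failure.

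What the reply leaves open is that the visit list permits what 8.2.2 does not, that Visit 2 has no randomisation step, and that nothing explicitly ties the envelope to results on file. The data review under blind that 8.1.3 calls for cannot undo a decision already taken at the site with the arm known.

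**Conclusion.** The point holds as an inconsistency in the stated time of randomisation, with an avoidable route to exclusions made with the arm known. It is worth correcting because the remedy costs almost nothing. It is not evidence that randomisation was or will be mistimed, and the sample size is not in error.

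The number affected cannot be estimated from the documents. The only ceiling is the all-cause allowance of 17 per arm. A lost success barely moves an arm's rate, so harm would require exclusions that differ between arms in number and in prognosis. The conclusion assumes that some sites work from the visit list. The visit mark on the randomisation row of the flow charts cannot be read in the available text, so which visit they assign is left open.

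**What to change.** Remove step (3) from 8.2.7.1, or move it after the tests and restrict it to Day 0. State the rule in 8.2.2 and 8.2.3, and make the flow charts agree: the envelope is opened on Day 0, as close to surgery as practicable, and only when all results bearing on the exclusion criteria are on file. Patients who fail before that point are recorded as screen failures and are not counted as randomised drop-outs.

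The cost is wording, plus having the envelope keeper available on the day of surgery. The envelopes, the keeper and the 1:1 stratified-block scheme do not change.

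If subjects have already been enrolled under this text, 8.2.3 has the keeper date each envelope. That date can be compared with the dates of the eligibility results and of surgery, and randomised patients outside the FAS or PPS can be listed by arm with the reason.

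This change does not alter the treated-only FAS or the use of the PPS for efficacy, so losses arising during surgery remain possible.
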